10.7. Events of Clinical Interest Associated with Pembrolizumab

Selected non-serious and serious adverse events are also known as Events of Clinical Interest (ECI). ECIs for this trial include:

- An overdose of pembrolizumab, as defined in Section 6.9, that is not associated with clinical symptoms or abnormal laboratory results.
- An elevated AST or ALT lab value that is greater than or equal to 3X the upper limit of normal and an elevated total bilirubin lab value that is greater than or equal to 2X the upper limit of normal and, at the same time, an alkaline phosphatase lab value that is less than 2X the upper limit of normal, as determined by way of protocol-specified laboratory testing or unscheduled laboratory testing.*

*Note: These criteria are based upon available regulatory guidance documents. The purpose of the criteria is to specify a threshold of abnormal hepatic tests that may require an additional evaluation for an underlying etiology

10.8. Expedited Safety Reporting to the Sponsor-Investigator

SAEs, ECIs, pregnancies and lactation exposure must be reported to the Sponsor-Investigator within 1 business day of awareness.

Reporting Period: SAEs and ECIs will be captured from the time of study treatment initiation/re-initiation through 90 days after the date of the last study treatment administration or 30 days if new anti-cancer therapy is initiated.

Exceptions:

- Reportable from informed consent:
 - Events that meet the definition of a SAE that are determined to be related and unexpected to a research procedure
 - Pregnancy and lactation; reportable through 120 days after last dose of pembrolizumab or 30 days if the subject initiates new anti-cancer therapy, whichever is earliest.
 - Events that meet the definition of an ECI (as defined per Section 10.7) if it causes the subject to be excluded from the trial, or is the result of a protocol-specified intervention, including but not limited to washout or discontinuation of usual therapy, diet, placebo treatment or a procedure (reportable until study treatment initiation).
- Reportable from study treatment initiation through duration of the subject's participation on the trial (treatment and follow-up):
 - Events occurring after the 30-day reporting period that are determined to be related to study treatment or a research procedure

SAEs will be followed until clinical recovery is complete and laboratory tests have returned to baseline, until progression has been stabilized, or until there has been acceptable resolution of the event. This may at times cause the follow-up period for SAEs to be greater than 90 days. Similarly, the Sponsor-Investigator is responsible for

following the subject during the required follow-up period even if the subject lives elsewhere or has been released from his or her care and is being treated under another service at LCI.

Please refer to Section 10.11 for the definition and expedited reporting requirements for ECI's.

10.9. Safety Reporting to the FDA

For investigator-initiated studies where the Sponsor-Investigator holds an IND, safety reporting requirements for the FDA apply in accordance with the regulations set forth in 21 CFR 312.32. The Sponsor-Investigator, or designee, will be responsible for notifying FDA (using a MedWatch form) and all participating Investigators of any unexpected fatal or life-threatening suspected adverse reaction as soon as possible, but in no case later than 7 calendar days after the Sponsor's initial receipt of the information. For all other serious and unexpected safety events, the Sponsor-Investigator, or designee, will notify the FDA within 15 calendar days.

It is the responsibility of the Sponsor-Investigator, Investigators and the Protocol Team to ensure SAEs are reported according to the Federal Regulations, ICH E6 Good Clinical Practices, the protocol guidelines, and Institutional Review Board reporting requirements.

Planned protocol deviations will be submitted to the FDA for prior approval only if the deviation affects the scientific validity of the study and/or the rights, safety, or welfare of subjects.

10.10. Safety Reporting to the IRB

All events occurring during the conduct of a protocol and meeting the definition of a UAP or SAE will be reported to the IRB per their reporting requirements.

Protocol deviations that, in the Investigator's judgment, potentially caused harm to participants or others or indicates that the participants or others are at an increased risk of harm, or has adversely impacted data integrity will be reported promptly to the IRB per their reporting requirements.

10.11. Safety Reporting to Merck

Any serious adverse event or ECI, or follow up to a serious adverse event or ECI, including death due to any cause other than progression of the cancer under study that occurs to any subject from the time of study treatment initiation/re-initiation through 90 days following cessation of study treatment, or 30 days if new anti-cancer therapy is initiated, whichever is earlier, whether or not related to pembrolizumab, will be reported within 2 working days of Sponsor-Investigator awareness to Merck Global Safety by the Sponsor-Investigator. SAEs that cause the subject to be excluded from the trial, or is a result of a protocol-specified intervention, including but not limited to washout or discontinuation of usual therapy, diet, placebo treatment or a procedure are

reportable to Merck from the time period beginning with informed consent until study treatment initiation/re-initiation. Pregnancies and lactations must be reported from informed consent through 120 days after last dose of pembrolizumab, or 30 days if the subject initiates new anti-cancer therapy, whichever is earliest.

Additionally, any serious adverse event, considered by an investigator who is a qualified physician to be related to pembrolizumab that is brought to the attention of the investigator at any time outside of the time period specified in the previous paragraph also must be reported immediately to the Sponsor-Investigator and to Merck.

SAE/ECI and pregnancy/lactation reports and any other relevant safety information are to be forwarded to Merck by the Sponsor-Investigator to Global Safety [contact]

If the Sponsor-Investigator holds an IND, a copy of all 15 Day Reports and Annual Progress Reports are to be submitted as required by the FDA or other local regulators. Investigators will cross reference this submission according to local regulations to the Merck Investigational Compound Number (IND, CSA, etc.) at the time of submission. Additionally, investigators will submit a copy of these reports to Merck & Co., Inc. (Attn: Worldwide Product Safety; [contact]) at the time of submission to the appropriate regulatory agency.

10.12. Protocol-Specific Exceptions to Serious Adverse Event Reporting

Efficacy endpoints as outlined in this section will not be reported to Merck unless there is evidence suggesting a causal relationship between pembrolizumab and the event. Any such event will be submitted to the Sponsor-Investigator within 24 hours and to Merck Global Safety within 2 working days either by electronic or paper media.

Specifically, the suspected/actual events covered in this exception include any event that is disease progression of the cancer under study.

The Sponsor-Investigator will monitor unblinded aggregated efficacy endpoint events and safety data to ensure the safety of the subjects in the trial.

Hospitalization related to convenience (e.g. transportation issues etc.) will not be considered a SAE.

11. MEASUREMENT OF EFFECT

11.1. Anti-tumor Effect – Solid Tumor

Response and progression will be evaluated in this study using the Revised Response Evaluation Criteria in Solid Tumors (RECIST) guideline version 1.1. Clinically stable

patients may continue to be treated beyond radiologic progression per the Investigator's discretion, however, at the time of RECIST-defined progression, progressive disease will be documented in the study records.

11.1.1. Methods for Evaluation of Measurable Disease

All measurements should be taken and recorded in metric notation using a ruler or calipers. All baseline evaluations should be performed as closely as possible to the beginning of treatment and never more than 4 weeks before the beginning of the treatment. Baseline evaluations prior to Second Course Phase will be performed per the investigator's discretion.

The same method of assessment and the same technique should be used to characterize each identified and reported lesion at baseline and during follow-up. Imaging-based evaluation is preferred to evaluation by clinical examination when both methods have been used to assess the anti-tumor effect of a treatment. The Sponsor-Investigator or designee will be responsible for performing tumor measurements. The tumor measurements will be recorded on the eCRF.

11.1.2. Response Criteria

Response will be evaluated using RECIST 1.1 criteria.⁴⁷

Complete Response:

- Target lesion: Disappearance of all target lesions. Any pathological lymph nodes (whether target or non-target) must have reduction in short axis to <10 mm.
- Non-target lesion: Disappearance of all non-target lesions. All lymph nodes must be non-pathological in size (<10 mm short axis).

Partial Response:

- Target lesion: At least a 30% decrease in the sum of diameters of target, taking as reference the baseline sum diameters.
- Non-target lesion: Not applicable

Stable Disease:

- Target lesion: Neither sufficient shrinkage to qualify for a partial response, nor sufficient increase to qualify for progressive disease, taking as reference the smallest sum diameters while on study.
- Non-target lesion: Not applicable.

Progressive Disease:

- Target lesion: At least a 20% increase in the sum of diameters of target lesions, taking as reference the *smallest sum on study* (this includes the

baseline sum if that is the smallest on study). In addition to the relative increase of 20%, the sum must also demonstrate an absolute increase of at least 5 mm. (*Note: the appearance of one or more new lesions is also considered progression*).

- Non-target lesion: *Unequivocal progression* (as described in RECIST version 1.1) of existing non-target lesions. (*Note: the appearance of one or more new lesions is also considered progression*).

Non-Complete Response / Non-Progressive Disease:

- Target lesion: Not applicable
- Non-target lesion: Persistence of one or more non-target lesion(s)

Table 8. Summary of RECIST 1.1 (Subjects with measurable disease)

Target Lesions	Non-target Lesions	New Lesions	Overall Response	Best Response for this Category also requires
CR	CR	No	CR	Documented at least once ≥ 4 weeks from baseline
CR	Non-CR/Non-PD	No	PR	Documented at least once ≥ 4 weeks from baseline
CR	Not evaluated	No	PR	
PR	Non-PD or not all evaluated	No	PR	
SD	Non-PD or not all evaluated	No	SD	Documented at least once ≥ 4 weeks from baseline
Not all evaluated	Non-PD	No	NE	N/A
PD	Any	Yes or No	PD	No prior SD, PR or CR
Any	PD*	Yes or No	PD	
Any	Any	Yes	PD	
* In exceptional circumstances, unequivocal progression in non-target lesions may be accepted as disease progression				
CR = Complete Response, PR = Partial Response, SD = Stable Disease, PD = Progressive Disease, and NE = inevaluable.				

Table 9. Summary of RECIST 1.1 (Subjects with non-measurable disease only)

Non-target Lesions	New Lesions	Overall Response
CR	No	CR
Non-CR/Non-PD	No	Non-CR/ Non-PD
Not all evaluated	No	NE
Unequivocal PD	Yes or No	PD
Any	Yes	PD

RECIST 1.1 will be adapted as follows to account for the unique tumor response seen in this class of therapeutics, **irRECIST**.

If imaging shows PD, tumor assessment should be repeated ≥ 4 weeks later in order to confirm PD with the option of continuing treatment for clinically stable subjects as discussed below in Table 10.

Clinically stable is defined by the following criteria:

- Absence of signs and symptoms indicating disease progression
- No decline in ECOG performance status
- Absence of rapid progression of disease
- Absence of progressive tumor at critical anatomical sites (e.g., cord compression) requiring urgent alternative medical intervention

Table 10. irRECIST: Imaging and Treatment after 1st Radiologic Evidence of PD

	Clinically Stable		Clinically Unstable	
	Imaging	Treatment	Imaging	Treatment
1 st radiologic evidence of PD	Repeat imaging at ≥ 4 weeks at site to confirm PD	May continue study treatment at the Investigator's discretion while awaiting confirmatory scan by site	N/A	Discontinue treatment
Repeat scan confirms PD	No additional imaging required	Discontinue treatment. In the event of confirmed progression, if the subject is clinically stable and in the investigator's opinion would derive clinical benefit from remaining on pembrolizumab, the subject may continue treatment beyond confirmed progression.	N/A No additional imaging required	N/A

Repeat scan shows SD, PR or CR	Continue regularly scheduled imaging assessments	Continue study treatment at the Investigator's discretion	N/A	N/A
--------------------------------	--	---	-----	-----

In determining whether or not the tumor burden has increased, decreased or stayed stable, site investigators should consider all target lesions as well as non-target lesions.

Any subject deemed clinically unstable should be discontinued from study regimen at first evidence of progressive disease by tumor imaging and is not required to have repeat tumor imaging for confirmation.

For a clinically stable subject with first radiologic evidence of progressive disease (i.e., unconfirmed progression of disease), it is at the discretion of the site investigator to continue treating the subject with the assigned treatment per protocol until progression of disease is confirmed at least 28 days from the date of the tumor imaging first suggesting PD. If progression is not confirmed on the subsequent tumor imaging, the subject should continue to receive study therapy and have tumor imaging performed every 6 weeks (\pm 7 days) to monitor disease status. If radiologic progression is confirmed by subsequent tumor imaging, then the subject will be discontinued from study treatment.

NOTE: If a subject with confirmed progression by tumor imaging (i.e. 2 scans at least 28 days apart demonstrating progressive disease) is clinically stable or clinically improved, and there is no further increase in the tumor burden at the confirmatory scan, an exception may be considered to continue treatment upon consultation with the Sponsor-Investigator. Subjects exhibiting unacceptable toxicity from trial therapy may NOT continue to receive trial therapy.

NOTE: In subjects who discontinue study therapy without first documented disease progression, every effort should be made to continue monitoring disease status by tumor imaging with a suggested interval of every 9 weeks in the first year and every 12 weeks (after year 1 per investigator discretion until (1) the start of new anti-cancer treatment, (2) documented disease progression (3) death, or (4) the end of the study, whichever occurs first. The same imaging modality (i.e. CT or MRI), acquisition and technical parameters should be used throughout the study for a given subject.

12. STATISTICAL CONSIDERATIONS

12.1. Sample Size

This study is primarily designed to assess the safety of doxorubicin (60-75 mg/m²) and pembrolizumab (200 mg) in previously treated or untreated subjects with

unresectable or metastatic soft tissue sarcoma. Based on the Bayesian stopping rules described in Section 12.5, 30 subjects will enable an assessment regarding whether or not the severe or life-threatening treatment emergent adverse event rate convincingly exceeds 0.55.⁴⁸

12.2. Endpoint Definitions

12.2.1. Severe or Life-Threatening Adverse Event

Severe or life threatening adverse event will be determined for each subject indicating whether or not the event meets all criteria listed below:

- Meets the definition of seriousness as defined in Section 10.6, and
- Pembrolizumab-related or doxorubicin-related toxicity per the Sponsor-Investigator and
- Considered to be clinically significant by the Sponsor-Investigator as to contribute to the stopping rule.

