10.3. Evaluation of Adverse Events

A qualified investigator will evaluate all adverse events according to the NCI Common Terminology for Adverse Events (CTCAE), version 4.0.

Reporting period: AEs will be captured from the time of treatment initiation/re-initiation through 30 days following cessation of study treatment.

Exception:

- Adverse events that meet the definition of an Event of Clinical Interest (ECI) as defined in Section 10.11 will be reportable from informed consent if the ECI causes the subject to be excluded from the trial, or is the result of a protocol-specified intervention including but not limited to washout or discontinuation of usual therapy, diet, placebo treatment or a procedure.

Please refer to Section 10.11 for the definition and expedited reporting requirements for ECI's.

Adverse events will be evaluated for relatedness to both doxorubicin and pembrolizumab.

All adverse events regardless of CTCAE grade must also be evaluated for seriousness. Adverse events will be evaluated according to Table 7.

Table 7. Adverse Event Evaluation

V4.0 CTCAE Grading	Grade 1	Mild; asymptomatic or mild symptoms; clinical or diagnostic observations only; intervention not indicated.
	Grade 2	Moderate; minimal, local or noninvasive intervention indicated; limiting age-appropriate instrumental ADL.
	Grade 3	Severe or medically significant but not immediately life-threatening; hospitalization or prolongation of hospitalization indicated; disabling; limiting self-care ADL.
	Grade 4	Life threatening consequences; urgent intervention indicated.
	Grade 5	Death related to AE
Seriousness	A serious adverse event is any adverse event occurring at any dose or during any use of study treatment that:	
	†Results in death; or	
	†Is life threatening; or places the subject, in the view of the investigator, at immediate risk of death from the event as it occurred (Note: This does not include an adverse event that, had it occurred in a more severe form, might have caused death.); or	
	†Results in a persistent or significant disability/incapacity (substantial disruption of one’s ability to conduct normal life functions); or	

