12.5. Primary Analysis

A maximum of 30 evaluable subjects with soft tissue sarcoma will be enrolled as a single cohort. It is not anticipated that the addition of pembrolizumab to standard chemotherapy will increase the rate of severe or life-threatening toxicity. It has been reported that the rate of any severe or life-threatening toxicity of doxorubicin and dacarbazine every 3 weeks is 55%⁴⁸.

If it becomes evident that the rate of severe or life-threatening toxicity convincingly exceeds 55%, enrollment to the study will be halted.

The stopping rule will hold enrollment if the posterior probability of severe or life-threatening toxicity risk exceeding 0.55 is 75% or higher. In this event, data will be evaluated to inform the subsequent conduct of the study. The prior for this monitoring rule is beta (11,9). This means that our prior assumption regarding the proportion of severe or life-threatening toxicity is 0.55, and there is 90% probability that this proportion is between 0.368 and 0.726. The operating characteristics of the stopping rule are given in Table 11 and are based on 5000 simulations:

Table 11. Operating characteristics of the stopping rule

Number of Subjects with Severe or Life-Threatening Toxicities	Max. Denominator Cutoff for Early Stopping	Posterior Probability: $\Pr(\text{Risk} > 0.55 \text{Data})$
4	4	0.7834
5	6	0.7536
6	7	0.8056
7	9	0.7728
8	11	0.7694
9	13	0.7558
10	14	0.7944
11	16	0.7812
12	18	0.7592
13	19	0.8002
14	21	0.7818
15	23	0.7710
16	25	0.7594
17	26	0.7988
18	28	0.7828
19	30	0.7706

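### The primary safety endpoint is defined by seriousness while its 55% benchmark is a severity rate, so the stopping rule may lose much of its ability to detect excess toxicity

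*Combined protocol and SAP*

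**What the plan says.** Section 12.2.1 determines the endpoint for each subject by "indicating whether or not the event meets all criteria listed below". The three criteria are:

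1. "Meets the definition of seriousness as defined in Section 10.6"
2. "Pembrolizumab-related or doxorubicin-related toxicity per the Sponsor-Investigator and"
3. "Considered to be clinically significant by the Sponsor-Investigator as to contribute to the stopping rule"

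No grade appears among them.

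Section 12.5 gives the benchmark: "It has been reported that the rate of any severe or life-threatening toxicity of doxorubicin and dacarbazine every 3 weeks is 55" per cent. That figure is both the threshold in the stopping rule and the mean of the Beta(11,9) prior. Section 12.1 says that 30 subjects will allow an assessment of "whether or not the severe or life-threatening treatment emergent adverse event rate convincingly exceeds 0.55", without mentioning seriousness, attribution or judgment. The primary objective in Section 1.1 is also worded by severity and calls for a comparison with a historical control.

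Table 7 in Section 10.3 describes Grade 3 as "Severe or medically significant but not immediately life-threatening" and Grade 4 as life-threatening. The same section requires every event to be assessed for seriousness whatever its grade. Section 10.6 defines seriousness mainly by outcome: death, immediate risk of death, admission, disability and similar. It adds other important medical events, with blood dyscrasias that do not lead to admission as one example.

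**The concern.** The name of the endpoint, the objective and the benchmark all refer to severity. The operational definition refers to seriousness and then applies two further filters. A subject with Grade 3 or 4 toxicity that is not also serious, related and judged significant is not counted, whereas the benchmark as worded covers any toxicity of that severity. No section reconciles the two definitions or gives an expected rate for the event as defined in 12.2.1.

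Two things are at stake. The primary comparison with the historical 55% may lean towards finding no excess toxicity. And the only numerical toxicity rule in the protocol may fail to hold enrollment at severe-toxicity rates it was set up to detect.

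**Working it through.** **1. The two definitions side by side**

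| Feature | Counted event (12.2.1) | Benchmark (12.5; Protocol Summary, item I) |
|---|---|---|
| Scale | Seriousness per 10.6, no grade | Severity: severe or life-threatening |
| Attribution | Related to either drug | Called toxicity; attribution rule not given |
| Discretion | Sponsor-Investigator judges whether it counts | None described |
| Exposure | Up to 35 pembrolizumab administrations (6.11) | Median of 3 courses |

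**2. Reproducing the rule.** Inputs from 12.5 are the Beta(11,9) prior, threshold 0.55, a hold if the posterior probability is at least 0.75, and a maximum of 30 subjects. After x events in n subjects the posterior is Beta(11+x, 9+n−x), and the rule holds if Pr(p > 0.55) ≥ 0.75.

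- Prior mean: 11/20 = 0.55. Prior 90% interval: 0.368 to 0.726, as stated.
- 4/4 gives Beta(15,9): exact 0.7797, printed 0.7834.
- 19/30 gives Beta(30,20): exact 0.7671, printed 0.7706.
- The largest gap is at 7/9: exact 0.7865, printed 0.7728. With 5000 simulations the standard error is about √(0.77×0.23/5000) = 0.006, so the printed values are consistent with simulation noise.
- The cutoffs agree in 15 of 16 rows. At 9/13 the exact posterior is 0.7488, just under 0.75.

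The rule is therefore understood correctly. Table 11 is titled as operating characteristics but gives only cutoffs and posteriors, with no hold probabilities by true rate.

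**3. Hold probability by rate of the counted event.** Let a(n,x) be the probability of reaching n subjects with x events and no hold so far. For counted rate p, a(n,x) = p·a(n−1,x−1) + (1−p)·a(n−1,x). Any state with posterior ≥ 0.75 is then moved to hold. Summing the held probability over n = 1 to 30, with a look after each subject (12.4.1 specifies continuous assessment), gives:

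| Counted rate | Probability of a hold |
|---|---|
| 0.30 | 1.9% |
| 0.35 | 4.2% |
| 0.40 | 8.4% |
| 0.45 | 15.9% |
| 0.50 | 27.7% |
| 0.55 | 43.8% |
| 0.60 | 62.2% |
| 0.70 | 91.2% |
| 0.75 | 97.4% |

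Using the printed cutoffs of Table 11 instead changes each figure by less than one percentage point.

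**4. Effect of under-counting.** Let T be the true rate of severe toxicity and f the share of affected subjects who meet all three criteria. The documents do not give f, so this is an assumption shown over a range. Ignoring low-grade serious events, the counted rate is T × f.

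| f | T = 0.70: counted rate, hold | T = 0.80: counted rate, hold |
|---|---|---|
| 1.0 | 0.70, 91.2% | 0.80, 99.6% |
| 0.8 | 0.56, 47.4% | 0.64, 76.1% |
| 0.7 | 0.49, 25.0% | 0.56, 47.4% |
| 0.6 | 0.42, 10.9% | 0.48, 22.4% |
| 0.5 | 0.35, 4.2% | 0.40, 8.4% |

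**5. Could low-grade serious events make up the loss?** If a share g of subjects without severe toxicity is counted through a lower-grade serious event, the counted rate is T·f + (1−T)·g. To restore 0.70 when T = 0.70:

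- f = 0.8 needs g = (0.70−0.56)/0.30 = 0.47.
- f = 0.6 needs g = (0.70−0.42)/0.30 = 0.93.

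Full compensation would need about half to nearly all of those subjects to have a related, serious, lower-grade event judged to count.

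**The case against.** The strongest reply is that seriousness under Section 10.6 is broad. It covers admissions, which Table 7 counts even when precautionary, and important medical events managed without admission. A reader might infer that Grade 4 neutropenia treated as an outpatient can never count. The documents do not support that: the blood dyscrasia example in 10.6 leaves such an event to medical judgment. Table 7's description of Grade 3 also mentions hospitalization and disability, so the two sets overlap. This stands, and it limits how large the gap can be said to be. It does not remove the gap, because 10.3 treats grade and seriousness as separate assessments and the third criterion can still exclude an event.

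Second, the direction depends on how the cited study counted its 55%, which cannot be seen here. Because the benchmark is called toxicity, the relatedness criterion may match it. Exposure here may be longer than the benchmark's median of 3 courses, and serious events are captured for 90 days after treatment (30 if new anti-cancer therapy starts; 10.8) against 30 days for other adverse events (10.3). Both could raise the counted rate. These points stand too, which is why under-counting is likely rather than certain.

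Third, other safeguards exist. Section 8.1 provides for regular review of events of all grades and submission of data to the monitoring committee, and 13.2 allows termination on safety findings. The rule in 12.5 is nevertheless the only numerical one. Finally, the wording in 12.1 is a one-sentence summary that refers to 12.5. It is better read as loose drafting to be aligned than as a separate endpoint.

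**Conclusion.** The mismatch is established from the text: the primary endpoint is counted by seriousness, relatedness and discretion, while its threshold and prior mean are taken from a severity rate. The likely effect is under-counting, and the rule can then lose much of its ability to detect excess toxicity. At an assumed true severe rate of 0.70, counting 80% of affected subjects takes the hold probability from 91% to 47%, and counting 60% takes it to 11%.

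A reader might go further and infer that the rule can almost never trigger, or that the safety stop is disabled. The documents do not support that. A hold probability below 5% needs a counted rate of about 0.35 or lower, roughly f = 0.5 at a true severe rate of 0.70, and no counted rate is given. At counted rates of 0.50 to 0.60 the rule still holds in 28% to 62% of trials. Confidence is high on the mismatch; the size of the loss is unknown. The calculations assume a look after every subject, with each outcome known at that look.

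**What to change.** In Section 12.2.1, replace the seriousness criterion with at least one treatment-emergent CTCAE v4 event of Grade 3 or higher per subject, related to pembrolizumab or doxorubicin. Delete the discretionary third criterion. Before adopting this, the sponsor should confirm from the cited source that the grade and attribution basis match how the 55% was counted; otherwise the change could create a new mismatch. State the capture window as well, since 10.3 and 10.8 differ.

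Alternatively, keep the related serious event as the endpoint and replace 0.55 and the Beta(11,9) prior with a justified reference rate and prior for that event. The third criterion should still go.

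With either choice, use one definition in 1.1, 12.1, 12.2.1 and 12.5, and add hold probabilities across true rates to Table 11. If the grade-based definition is adopted, report related serious events separately under 12.7.

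The cost is a few wording changes and a short calculation. Events of all grades are already recorded in the eCRF (Section 10) with attribution (10.3.1), so no new data are needed. The downside of the grade-based version is that a hold is likely to become more frequent. The rule already holds 43.8% of the time when the counted rate is exactly 0.55, and the sponsor should see that figure before settling the definition.
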